2.4.2. CV Safety (MACE) Co-Primary Hypothesis

The co-primary CV safety objective will assess the estimand of time to first occurrence (in days) of adjudicated MACE from randomization to the end of study in all randomized subjects regardless of what treatment(s) they go on to receive. The primary analysis will test for non-inferiority of treatment with daprodustat relative to darbepoetin alfa, expressed by the following statistical hypotheses:

- **Null:** daprodustat is inferior to darbepoetin alfa, with at least a 25% increased relative risk of first MACE (i.e. the hazard ratio is ≥ 1.25)
- **Alternative:** daprodustat is non-inferior to darbepoetin alfa (i.e. the hazard ratio is < 1.25)

The non-inferiority margin is pre-defined as the hazard ratio of 1.25; supported by a review of evidence reported in historical randomized trials of darbepoetin alfa in dialysis and non-dialysis CKD subjects and after consideration of the largest point estimate that, by design, would meet the statistical criterion for non-inferiority.

Statistical significance of non-inferiority will be assessed at the one-sided 2.5% level. A Cox-Proportional Hazards-Regression model, adjusting for treatment and prognostic randomization stratification factors (region and current ESA use), will be used to estimate the hazard-ratio, its two-sided 95% CI and to generate the p-value for the non-inferiority test. Non-inferiority will be achieved if the upper limit of the two-sided 95% CI is below the margin of 1.25.

The co-primary endpoints will be tested first. Non-inferiority needs to be established for both co-primaries to proceed to evaluate MACE for superiority as well as the principal secondary endpoints for superiority. Principal secondary endpoints include prioritized composites for MACE (including thromboembolic events and hospitalizations for HF) and progression of CKD. Statistical testing of MACE for superiority as well as the principal secondary endpoints will be adjusted for multiplicity (Section 10.11.1).

3. PLANNED ANALYSES

3.1. Interim Analyses

The IDMC will periodically receive unblinded safety reports containing, at a minimum, clinical endpoints (whether adjudicated or pending adjudication) and SAEs, from an independent Statistical Data Analysis Center (SDAC) while the study is ongoing. The IDMC may recommend stopping the study for safety at any time.

In addition, the IDMC will evaluate the co-primary MACE endpoint to assess for futility of achieving non-inferiority at study completion. Pre-specified guidelines governing the decision to continue or stop the study will consider signals for harm, the predictive probability of achieving at least non-inferiority at trial end and the risk of incorrectly stopping for futility. In addition to MACE, any decisions regarding futility will take into account data related to: 1) components of MACE, 2) endpoints describing BP, 3) other safety and efficacy data across the daprodustat clinical program, 4) emerging data in the public domain pertaining to safety or efficacy of HIF-prolyl hydroxylase inhibitors, and 5) any other data considered to be relevant by the IDMC. The IDMC will make a recommendation to GSK and the ESC chair as outlined in the IDMC charter regarding whether the study should continue unchanged, be modified or be terminated.

There are no prospectively defined interim analyses planned to stop the study early for benefit. While the planned futility analysis will have a small impact on reducing study-wise Type I error rate, there are no plans to adjust the alpha level used for the final analysis.

Further details of futility rules and analysis timings will be provided in the IDMC Charter.

3.1.1. Additional Considerations at the Interim Analysis Not Specified in the Protocol

If the study stops because of results of an interim analysis, subjects will be brought to the investigational sites for the final study visits (end of study visit and follow-up visit) as soon as possible.

If the trial is stopped for increased MACE risk, futility or other safety concerns, point estimates, two-sided 95% confidence intervals, and one-sided p-values will be generated for the primary and principal secondary endpoints. One-sided p-values will be compared to 0.025 to assess nominal significance, and will be provided for descriptive purposes only.

3.2. Final Analyses

The final planned primary analyses will be performed after the completion of the following sequential steps:

1. It is projected that the target number of events has been attained as defined in the protocol, and final study clinic visits have occurred.
2. All required database cleaning activities have been completed and final database release and database freeze has been declared by PPD Data Management.
3. All criteria for unblinding the randomization codes have been met.
4. Randomization codes have been distributed according to GSK and PPD procedures.

4. ANALYSIS POPULATIONS

Inclusion in any analysis population is contingent on a subject signing informed consent.

Population	Definition / Criteria	Analyses Evaluated
Screened	
 All screened subjects. 	
 Study Population Safety
Intent-To-Treat (ITT)	
 All randomized subjects. Subjects will be analyzed according to the treatment to which they were randomized. 	
 Study Population Efficacy Safety
Enrolled	
 All randomized subjects. Subjects will be analyzed according to the treatment to which they were randomized. Use of the enrolled population is required for some displays; for this study, the enrolled and ITT populations will be identical. 	
 Study Population
Per-Protocol (PP)	
 All ITT subjects without PP population exclusions. Exclusions from the PP population are defined in Section 4.1 (Protocol Deviations and Study Population Exclusions) and Section 10.1 (Protocol Deviation Management and Definition for Per-Protocol Population). Subjects will be analyzed according to the treatment received.¹ 	
 Efficacy

Population	Definition / Criteria	Analyses Evaluated
Safety	
 All randomized subjects who receive at least one dose of randomized treatment. Subjects will be analyzed according to the treatment received.¹ 	
 Safety
Sub-study Populations		
Please see sub-study analysis plans for definitions of sub-study analysis populations.		

[1]: Only subjects receiving incorrect randomized treatment for the duration of their study participation will be analyzed according to the treatment received. Otherwise, subjects will be analyzed according to the treatment to which they were randomized.

4.1. Protocol Deviations and Study Population Exclusions

- Significant protocol deviations will be summarized and listed.
- Exclusions from the main study populations described above will also be summarized and listed. Please refer to [Appendix 1: Protocol Deviation Management and Definitions for Per-Protocol Population](#) for further details of Per-Protocol population exclusions.
- Protocol deviations and study population exclusions will be tracked by the study team throughout the conduct of the study in accordance with PPD's Deviation Management Plan and Study Deviation Rules Document.
 - Data will be reviewed prior to unblinding the database to ensure all significant deviations and deviations which may lead to exclusion from the analysis are captured and categorized on the protocol deviations dataset.
 - This dataset will be the basis for the summaries and listings of protocol deviations.
- A separate summary and listing of all inclusion/exclusion criteria deviations will also be provided. This summary will be based on data as recorded on the inclusion/exclusion page of the electronic case report form (eCRF).

5. CONSIDERATIONS FOR DATA ANALYSES AND DATA HANDLING CONVENTIONS

Table 1 provides an overview of appendices within the RAP for outlining general considerations for data analyses and data handling conventions.

Table 1 Overview of Appendices

Section	Component
Section 10.1	Appendix 1: Protocol Deviation Management and Definitions for Per-Protocol Population
Section 10.2	Appendix 2: Time & Events
Section 10.3	Appendix 3: Assessment Windows
Section 10.4	Appendix 4: Treatment States and Phases
Section 10.5	Appendix 5: Data Display Standards & Handling Conventions
Section 10.6	Appendix 6: Derived and Transformed Data
Section 10.7	Appendix 7: Premature Withdrawals & Handling of Missing Data
Section 10.8	Appendix 8: Values of Potential Clinical Importance
Section 10.9	Appendix 9: Multicenter Studies
Section 10.10	Appendix 10: Examination of Covariates, Subgroups & Other Strata
Section 10.11	Appendix 11: Multiple Comparisons & Multiplicity
Section 10.12	Appendix 12: Model Checking and Diagnostics for Statistical Analyses

6. STUDY POPULATION ANALYSES

6.1. Overview of Planned Analyses

The study population analyses will be based on the ITT population and will include a total column, unless otherwise specified.

Table 2 provides an overview of the planned study population analyses.

Table 2 Overview of Planned Study Population Analyses

Parameter	Analysis Population	Data Displays Generated		
		Table	Figure	Listing
Populations Analyzed				
Study Populations	Screened	Y		
Screening Status and Reasons for Screen Failure	Screened	Y		Y
Screening Attempts	Screened	Y		
Exclusions from Study Populations	ITT	Y		Y
Subject Disposition				
Subjects Who Were Rescreened	Screened			Y
Subject Status and Reasons for Study Withdrawal at Wk28, Wk52 and End of Study	ITT	Y	Y	Y
Subject Status and Reasons for Study Withdrawal at Wk28, Wk52 and End of Study by Region	ITT	Y		
Subject Status and Reasons for Study Withdrawal at Wk28, Wk52 and End of Study by Country	ITT	Y		
Treatment Status and Reasons for Discontinuation of Randomized Treatment at Wk28, Wk52 and End of Study	ITT	Y	Y	Y
Treatment Status and Reasons for Discontinuation of Randomized Treatment at Wk28, Wk52 and End of Study by Region	ITT	Y		
Treatment Status and Reasons for Discontinuation of Randomized Treatment at Wk28, Wk52 and End of Study by Country	ITT	Y		
Number of Subjects by Region, Country and Site ID	Enrolled	Y		
Type of Subject Contact at Wk28, Wk52 and End of Study	ITT	Y		
End of Study Contact	ITT	Y		
Subject Follow-up Time	ITT	Y		
Subject Completion Status	ITT	Y		
Subject Survival Status	ITT	Y		
Planned and Actual Treatments	ITT			Y
Protocol Deviations				
Significant Protocol Deviations	ITT	Y		Y
Subjects with Inclusion/Exclusion Criteria Deviations	ITT	Y		Y
Demographic & Baseline Characteristics				
Demographic & Baseline Characteristics	ITT & Safety	Y		Y
Demographic & Baseline Characteristics by Prior ESA Use	ITT	Y		
Age Ranges	Enrolled	Y		
Race and Racial Combinations	ITT	Y		Y
Smoking history	ITT	Y		
Medical Conditions	ITT	Y		

Parameter	Analysis Population	Data Displays Generated		
		Table	Figure	Listing
Dialysis Modality and Frequency	ITT	Y		
Dialysis Modality Changes	ITT	Y		
Dose Information During Transition to Dialysis	ITT	Y		
Prior and Concomitant Medications				
Pre-Treatment Medications	ITT	Y		
On-Treatment Medications	ITT	Y		Y
Post-Treatment Medications	ITT	Y		
Non-randomized ESA Use During Treatment Period	Safety	Y		Y
Exposure and Randomized Treatment Compliance				
Extent of Exposure to Randomized Treatment	Safety	Y		Y
Randomized Treatment Compliance Categories	Safety	Y		
Randomized Treatment Compliance	Safety	Y		
IRT and eCRF Dose and Frequency Discrepancies	Safety	Y		

NOTES:

- Y = Yes display generated.

6.2. Display Details

6.2.1. Populations Analyzed

The number of subjects in the Screened, Safety, ITT, Enrolled, PP and relevant sub-study populations will be summarized by treatment group and overall.

The number and percentage of subjects by screening status (enrolled/randomized, screen failed) and associated reasons for screen failure will be summarized for the screened population.

A summary of all screening attempts and associated reasons for screen failure will be provided for the screened population. This summary will count each screening attempt individually, regardless of whether or not there was a subsequent re-screen.

A listing of screen failure records will be provided for all subjects who failed screening, including site ID, unique subject ID, date of screen failure, and reason(s) for screen failure.

The number and percentage of subjects excluded from the Safety and PP populations will be summarized by reason, treatment group and overall in individual displays for each study population.

A listing of subjects excluded from the Safety and PP populations will be provided. The listing will include the treatment arm, site ID, unique subject ID, date of deviation, study day of deviation, category, coded term, criteria which lead to exclusion, and the populations from which the subject was excluded.

6.2.2. Subject Disposition

The summary of subject status and reasons for study withdrawal will include:

- the number and percentage of subjects ongoing at the Week 28 visit and Week 52 visit, the associated randomized treatment status (on randomized treatment or in follow-up), the number and percentage of subjects withdrawing early before the Week 28 visit and the Week 52 visit, the associated reasons/subreasons for withdrawal, and the number and percentage of subjects that died before the Week 28 visit and Week 52 visit, summarized by treatment group and overall. For subjects with an adverse event leading to withdrawal of consent, the outcome (fatal, non-fatal) of the adverse event will be summarized.
- the overall number and percentage of subjects who completed the study, the overall number and percentage of subjects withdrawing early from the study and the associated reasons/subreasons for withdrawal summarized by treatment group and overall. For subjects with an adverse event leading to withdrawal of consent, the outcome (fatal, non-fatal) of the adverse event will be summarized.

The summary of subject status and reasons for study withdrawal will be repeated by region and by country. The overall only summary of subject status and reasons for study withdrawal will be repeated by relationship to COVID-19 pandemic.

A listing of reasons for study withdrawal will be provided for all subjects who were withdrawn from the study. This listing will include treatment, site ID, unique subject ID, date of withdrawal, study day of withdrawal, primary reason for withdrawal, subreason for withdrawal, was a follow-up phone contact attempted 3 times, and was a follow-up certified letter mailed.

A listing of screening status will be provided for all subjects who were rescreened for the study. The listing will include unique subject ID, subject ID, screening status, date of screen failure, and reason for screen failure.

The summary of treatment status and reasons for discontinuation of randomized treatment will include:

- the number and percentage of subjects who never received randomized treatment at the Week 28 and Week 52 visits, the number and percentage of subjects ongoing on randomized treatment at the Week 28 and Week 52 visits, and the number and percentage of subjects who discontinued randomized treatment, including the breakdown of the number and percentage of subjects who died while taking randomized treatment and those that did not die while taking randomized treatment, and the associated reasons/subreasons for randomized treatment discontinuation overall and separately for subjects who did not die while taking randomized treatment and for subjects who died while taking randomized treatment at the Week 28 and Week 52 visits summarized by treatment group and overall.

- the overall number and percentage of subjects who never received randomized treatment, the overall number and percentage of subjects who prematurely discontinued randomized treatment during the study, including the breakdown of the number and percentage of subjects who died while taking randomized treatment and those that did not die while taking randomized treatment, and a summary of the reasons and subreasons for randomized treatment discontinuation overall and separately for subjects who died while taking randomized treatment and for subjects who did not die while taking randomized treatment, and the overall number and percentage of subjects who did not prematurely discontinue randomized treatment during the study summarized by treatment group and overall.

The summary of treatment status and reasons for discontinuation of randomized treatment will be repeated by region and by country. The overall only summary of subject status and reasons for discontinuation of randomized treatment will be repeated by relationship to COVID-19 pandemic.

The number of subjects will be summarized by Country, Site Id. and Investigator Id. for two periods – pre COVID-19 pandemic and during COVID-19 pandemic. This summary will be produced based on the enrolled population. The total column, summarizing subjects regardless of treatment, will be included. Rows will be sorted alphabetically by country, then in numerical order by Site ID.

The Start Dates of COVID-19 Pandemic Measures will be provided by country in a listing.

A listing of the randomized treatment discontinuation record will be provided for all subjects who prematurely discontinued randomized treatment. This listing will include treatment, site ID, unique subject ID, date of last dose, study day of discontinuation, primary reason for discontinuation, and subreasons for discontinuation.

A Kaplan-Meier plot of time to early withdrawal from the study will be produced by treatment group.

Two Kaplan-Meier plots of time to permanent randomized treatment discontinuation by treatment group will be produced. For both of the plots, the risk set will include all subjects who started taking randomized treatment. The first plot will consider an event as subjects who discontinued randomized treatment and the second plot will consider an event as subjects who discontinued randomized treatment and did not die while on treatment. If a subject discontinued treatment due to death, that subject will not count towards the event, and will be censored instead.

The number and percentage of subjects by region, country, site ID and investigator name will be summarized by treatment group and overall for the enrolled population.

The type of subject contact at the Week 28, Week 52 visit and End of Study visit will be provided by treatment group and overall.

A summary of the timing of the end of study contact will be provided by subject status, type of contact, treatment group and overall.

A summary of the total follow-up time and percentage of total possible follow-up time during time periods of the study (i.e., time period for follow-up of CV endpoints, time period for vital status, and time period for on-treatment CV endpoints) will be provided by treatment group and overall (see Section 10.6.2 and Section 10.6.4 for definitions).

A summary of the subject completion status, including the number and percentage of subjects included in the co-primary Hgb analysis, by CV endpoint status (known and unknown at the end of study) and by vital status (known and unknown at the end of study) will be provided by treatment group and overall.

A summary of the subject survival status by study completion status will be provided by treatment group and overall.

A listing of planned and actual treatments will be provided. This listing will include region, country, site ID, investigator name, subject number, randomization number, randomization date, randomized treatment, actual treatment flag.

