10.6. Appendix 6: Derived and Transformed Data

10.6.1. General

Multiple Measurements at One Time Point

- Mean of the measurements will be calculated and used in any derivation of summary statistics but if listed, all data will be presented.
 - Triplicate BP and HR measurements are expected at certain time points (See Section 10.2.1)
- Subjects having both High and Low values for Normal Ranges at any post-baseline visits for safety parameters will be counted in both the High and Low categories of “Any visit post-baseline” row of related summary tables. This will also be applicable to relevant Potential Clinical Importance summary tables.

Randomization Date

- Date subject was randomized

Treatment Start Date

- First randomized treatment dose start date

Last Non-Zero Dose Date

- Date of last actual dose of randomized study treatment from the IP Discontinuation eCRF form.
 - The dose steps used by the dosing algorithm described in the protocol include a dose hold or a zero dose. If subjects are assigned by the algorithm to a zero dose, they do not receive randomized treatment for that period. Hence, it would be possible for a subject to complete the study, while still following the dosing algorithm, but not actually be taking any actual randomized treatment. The last non-zero dose date, then captures the latest date in the study that a subject physically took a dose of randomized treatment.
- The eCRF allows for the possibility of partial or missing dates to be recorded for the last actual dose of randomized study treatment on the IP Discontinuation form (i.e., missing day, or day and month, or day and month and year). In such a case, or in case of subjects who have a non-missing treatment start date, but are missing an IP Discontinuation form, the following conventions will be applied in order to impute a last non-zero dose date:
 - Missing day:
 - The last day of the month will be used, unless the treatment stop date also occurs in the same month; in this case, the treatment stop date will be used.
 - Missing day and month;
 - ‘31’ will be used for the day and ‘Dec’ will be used for the month, unless the treatment stop date also occurs in the same year; in this case the treatment stop date will be used.
 - Missing day, month, and year:
 - Treatment stop date will be used only for subjects who have a non-missing treatment start date.

Treatment Stop Date

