- Calculated as the latest randomized treatment dose stop date for subjects who have a non-missing treatment start date. Note that this date could come from a randomized treatment exposure record with a missing or partial dose stop date if the associated dose start date for that exposure record is on or after the last non-missing randomized treatment dose stop date.
- The eCRF allows for the possibility of missing or partial dates to be recorded for the dose stop date on the study treatment form (i.e., missing day, or day and month, or day and month and year). In such a case, the following conventions will be applied in order to impute a treatment stop date:
 - Missing day:
 - The last day of the month will be used, unless the study completion or withdrawal date also occurs in the same month; in the case, the study completion or withdrawal date will be used.
 - Missing day and month:
 - '31' will be used for the day and 'Dec' will be used for the month, unless the study completion or withdrawal date also occurs in the same year; in this case, the study completion or withdrawal date will be used.
 - Missing day, month and year:
 - The study completion or withdrawal date will be used only for subjects who have a non-missing treatment start date.

End of Treatment Value

- Only defined for subjects with a non-missing treatment start date
- Hgb, iron, transfusion and PRO parameters: the latest value on or before the treatment stop date + 1 day.
- Blood pressure, central laboratory, and vital signs parameters: the latest value on or before the last non-zero dose date + 1 day.

Study Completion/Withdrawal Date

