10.6.2.3. Randomized Treatment Discontinuation, Study Withdrawal and Possible Follow-up Time

Randomized Treatment Discontinuation, Study Withdrawal, and Possible Follow-up Time
Randomized Treatment Discontinuation

 ● $\text{Randomized Treatment Discontinuation Censored Time (days)} = \text{Treatment stop date} - \text{Treatment start date} + 1$ If the treatment stop date = death date for a subject, the subject will be censored and will not be counted as an event for treatment discontinuation summaries that exclude subjects who die while on treatment. ● $\text{Time to Randomized Treatment Discontinuation (days)} = \text{Treatment stop date} - \text{Treatment start date} + 1$ ● $\text{Randomized Treatment Person Years} = (\text{Cumulative total of time to randomized treatment discontinuation for subjects who discontinued randomized treatment} + \text{Cumulative total of randomized treatment discontinuation censoring time for subjects who did not discontinue randomized treatment}) / 365.25$ ● $\text{Randomized Treatment Discontinuation Incidence Rate (per 100 person years)} = 100 * \text{Number of subjects who discontinued randomized treatment} / \text{randomized treatment person years}$
Study Withdrawal

 ● $\text{Study Censored Time (days)} = \text{Study completion date} - \text{Randomization date} + 1$ ● $\text{Time to Study Withdrawal (days)} = \text{Study withdrawal date} - \text{Randomization date} + 1$ ● $\text{Study Person Years} = (\text{Cumulative total time to study withdrawal for subjects withdrawing from the study} + \text{Cumulative total of study censoring time for subjects who did not withdraw from study}) / 365.25$ ● $\text{Study Withdrawal Incidence Rate (per 100 person years)} = (100 * \text{Number of subjects who have withdrawn from study}) / \text{Study Person Years}$

Randomized Treatment Discontinuation, Study Withdrawal, and Possible Follow-up Time
Possible Follow-up Time

 • Possible follow-up time (days) = Study completion date or date of the middle of the end of study window for subjects who did not complete the study – randomization date + 1 • Total possible follow-up time (person years) = Cumulative total of possible follow-up time (days) for all subjects / 365.25

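### The second discontinuation plot is meant to censor subjects who stop because of death, but the derivation does so only when the treatment stop date equals the death date

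*SAP*

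**What the plan says.** SAP 6.2.2 (Subject Disposition) plans two Kaplan-Meier plots of permanent discontinuation among subjects who started randomized treatment. For one, "The first plot will consider an event as subjects who discontinued randomized treatment". For the other, "the second plot will consider an event as subjects who discontinued randomized treatment and did not die while on treatment". The next sentence gives the handling of deaths: "If a subject discontinued treatment due to death, that subject will not count towards the event, and will be censored instead".

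The tables in the same section also report "the breakdown of the number and percentage of subjects who died while taking randomized treatment", with a matching group who did not die, and reasons for stopping shown overall and within each group.

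SAP 10.6.2.3 supplies the derivation: "If the treatment stop date = death date for a subject, the subject will be censored and will not be counted as an event". It is limited to "treatment discontinuation summaries that exclude subjects who die while on treatment".

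SAP 10.6.1 defines the treatment stop date from the exposure records: "Calculated as the latest randomized treatment dose stop date for subjects who have a non-missing treatment start date". It keeps this apart from the last non-zero dose date: "Date of last actual dose of randomized study treatment from the IP Discontinuation eCRF form".

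**The concern.** The sentence in 6.2.2 is a rule about cause. The derivation in 10.6.2.3 is a test of whether two dates coincide. They agree only if the site closes the last exposure record on the day of death. Where the record closes a day or more earlier, a subject who never chose to stop, and was never taken off treatment, enters the second plot as a discontinuation.

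That plot is there to show how long subjects stay on drug when death is set aside, which matters in an open-label trial. Deaths left in as events overstate voluntary or tolerability-driven stopping. The clinical study report could also disagree with itself: the same death could be an on-treatment event in the while-on-treatment MACE analysis, while the disposition display shows the subject as having stopped without dying on treatment.

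**Working it through.** The SAP gives no figure to reproduce, so the check sets the rules side by side and runs one example through them.

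**Rules used**
- Discontinuation time and censoring time (10.6.2.3) share one formula: treatment stop date − treatment start date + 1.
- Status (10.6.2.3): censored if treatment stop date = death date; otherwise an event.
- On treatment for Hgb, iron, transfusion and PRO data (10.4.1.1): up to treatment stop date + 1 day.
- On treatment for CV endpoints, deaths included (10.4.1.2): up to last non-zero dose date + 28 days.

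**Example**, treatment start on Day 1, subject on treatment until death:

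| Stop date | Death date | Time (days) | Status under 10.6.2.3 | Intended status under 6.2.2 |
|---|---|---|---|---|
| Day 200 | Day 200 | 200 − 1 + 1 = 200 | Censored | Censored |
| Day 200 | Day 201 | 200 − 1 + 1 = 200 | Event | Censored |

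Only the status changes, not the time. In any discontinuation rate computed with deaths excluded, each such subject adds one to the numerator and leaves the person-years unchanged.

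**The same Day 201 death under the other definitions**
- 10.4.1.1: 200 + 1 = 201, so Day 201 is on treatment.
- 10.4.1.2: on treatment if the last non-zero dose was on or after Day 201 − 28 = Day 173.

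Those windows were written for other data and do not govern disposition. They do show that the equality test is narrower than any meaning of on-treatment that the SAP uses for post-baseline data.

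**Two further weaknesses of an exact match**
- SAP 10.6.4.1 carries two death dates, one from the eCRF death page and one from the endpoint committee. 10.6.2.3 does not say which is compared.
- Partial dates are imputed by different rules. A death with a missing day goes to the first of the month or the latest known contact or event (10.6.4.1). A stop date with a missing day goes to the end of the month or the study completion/withdrawal date (10.6.1). Imputation can therefore break a true match, and can also create one.

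**What cannot be computed.** The SAP does not say how exposure records are closed when a subject dies and gives no count of on-treatment deaths. The number misclassified is unknown.

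**The case against.** The best defence is that 6.2.2 also words the event as not dying while on treatment, and that equal dates are a prespecified, reproducible definition of that phrase. That much is fair: the two sections can be read as a broad statement and a narrow definition. It does not rescue the next sentence, which censors subjects who stopped due to death, because a date match cannot deliver that.

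Several other points for the plan stand:
- The test uses the exposure-record stop date, not the last dose taken. A record can run past the last tablet or injection, so a gap between last dose and death does not by itself break the match.
- A fully missing stop date, or a partial one in the same month or year, takes the study completion/withdrawal date. Subjects who die count as completers, so some records left open at death may match.
- The first plot counts every discontinuation by design, and the tables split rather than censor. The equality rule reaches the tables only through the word for summaries in 10.6.2.3.
- Recorded reasons for stopping are still tabulated overall and listed, so the safety endpoint on reasons for discontinuation is not itself altered.

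A reader might infer a bias between arms: if a 4-weekly darbepoetin record closed on the injection day, the dates would coincide in only about 1 death in 28, against far more often for a daily tablet. The SAP does not support this. Its compliance rules (10.6.2.5) treat a 4-weekly record of 15 to 42 days with one dose as compliant and class gaps between records as under-compliant, so records are expected to span dosing intervals. Section 10.6.3.6 has sites open exposure records on dosing instructions in both arms.

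**Conclusion.** The point holds in a limited form. The stated intent in 6.2.2 and the derivation in 10.6.2.3 do not match, and a death one or more days after the recorded stop date is misclassified in the second plot. The same error reaches the died / did-not-die table split if that split uses the rule.

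The size is unknown, and no difference between arms can be claimed in either direction. It would be wrong to infer any effect on the trial's conclusions: neither co-primary analysis, no principal secondary analysis and no hypothesis test uses this derivation. It is an inexpensive correction to descriptive displays. The conclusion assumes only that some sites will record a stop date before the date of death for a subject who had not been taken off treatment.

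**What to change.** In SAP 10.6.2.3, replace the equality test with a single died-on-treatment flag, defined the same way in both arms:

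1. The subject died, with no decision to discontinue permanently recorded before death.
2. Identify this from the recorded stop reason if the IP Discontinuation form captures death. The SAP does not show that it does, so check the form first. Time to rescue (10.6.3.3) already classifies stops by recorded primary reason and subreason.
3. If the form does not capture death, use death on or before a fixed window after the treatment stop date that is consistent with 10.4.1, for example stop date + 1 day. A window this short would still miss longer gaps, so the recorded reason is preferable. Do not tie the window to the dosing interval: that would make it longer for darbepoetin than for daprodustat and create a difference between arms by construction.
4. State whether the eCRF or the endpoint committee death date is used.
5. Apply the flag to both the second Kaplan-Meier plot and the died / did-not-die split in 6.2.2, and word the event the same way in both sections.

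The cost is a few lines of SAP text and one derived variable, settled before unblinding. It needs no new data if the form captures death or the window is used.
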